2.5 Treatment Allocation

Prior to the baseline visit, eligible participants will be randomly allocated in equal proportions to one of two treatment groups, oral inosine titrated to achieve trough serum urate in the range 7.1 to 8.0 mg/dL or placebo, according to a permuted-block randomization schedule, stratified by site. The randomization schedule was prepared by computer program by the unblinded study statisticians.

2.6 Treatment Administration

Study drug will be orally self-administered in capsules containing 500 mg of inosine (active drug) or lactose (placebo). Participants will take up to two capsules three times per day (i.e., up to 3.0 gm/day) based on individualized titration that aims to achieve trough serum urate in the range 7.1 to 8.0 mg/dL in the active arm and equivalent dosage adjustments in the placebo arm. Details of the titration algorithm are specified in the clinical protocol. Note, the maximum study drug dosage was reduced from 3.0 to 2.0 gm/day beginning 24 Jan 2018 based on safety concerns over a higher than expected rate of kidney stones with greatest incidence among participants on study drug dosages greater than 2.0 gm/day.

2.7 Allocation Concealment

The randomization schedule is known only by the unblinded study statisticians who generated the schedule and implement the titration algorithm and a calibrated urine alkalinization process and by the study drug distributor. Concealment of the true treatment allocation of specific participants is achieved by use of matched active and placebo capsules, matched titration schedules, and matched urine alkalinization rates. Clinical members of the Steering Committee, site investigators and other site staff, clinical coordination and data management staff, the medical monitor, and all participants are blinded to participant treatment allocations. The Data and Safety Monitoring Board (DSMB) members are provided treatment-specific information in order to monitor the trial but such information is masked by use of coded values to identify the treatment groups. The DSMB may request the true treatment identities.

Schedule of Assessments 2.8

ACTIVITY		SCREE	N		Wash-i	n –	TREATMENT (Period 1) Maintenance								w	WA SHOUT (Period 2)							
- 60 - 58 Day Interval to - 13 to - 11			- 52 to - 5	00	Week 3 21±3		Week 12	Month 6	Month 9	Month 12 360 ± 7	Month 15	Month 18	21	Month 24	Month 25 V10 + 30 ± 3	Month 25-26 V10 + 45 ± 15	Month 26 V10 +	Month 27	nła	nła	n/a	nła	
			DS1 ⁶	BL ⁶			84±7	180 ± 7	270 ± 7		450 ± 7	540±7	630±7	720 ± 7		45±15	60±3	27 V10+ 90±3	U01,	DF	T(vst #)		
Visit#/code	SC1	SC2	DSI	BL-	V01	V02	V03	√04	∨05	∨06	V07	\708	V09	V10	TE1	USZ.	TE2	SV	U02, etc.	DF	e.g.,T06	PW	
Written Informed Consent Consent for Optional Blood Sample Collection/Storage/Future Use ¹	× ±																						
Smart & SURE Consent, Registration, & Training ¹	_	±	±	±	±	±	±	±	±	±	±	±	±										
Consent for 2 nd DAT Scan ¹		_			_	_	_	_	_	±	±	±	±	±									
Assign Subject ID Number	×																						
Screening/Demographics	x																						
Socio-Economics				x																			
PD Risk Factors				×																			
Smoking, Alcohol and Caffeine Status				×																			
Inclusion/Exclusion	x	x		x																			
Medical History General		×																					
Vital Signs (orthostatics & weight)		x		x			x			x				x				x	±	x			
Height				x																			
Electrocardiogram		x								x				x						x			
General Neuro & Medical Exams		x																					
Blood Draw> Serum Urate ²	×	x		x	x	x	x	x	x	x	x	x	x	x				x	±	x			
Blood Draw> Chem 7 Panel ²		×		x	x	x	x	x	x	x	x	×	x	x				x	±	x			
Blood Draw> LFTs, TSH and Lipids ²				×			×							x					±	x			
Blood Draw> CBC ²				x	±	±	x	±	±	±	±	±	±	x					±	x			
Urine Collection> Analysis/Sediment ²	x			x	×	×	x	×	×	x	x	×	×	x				x	±	x			
Blood Draw> Biomarker Study ¹				±										±				±	±				
Most Revent Food Intake, Study Drug and PD Medication				×	x	×	×	×	×	x	×	×	×	×				_					
1 st DAT Scan ¹			±																				
2 nd DAT Scan ¹																±							
24 Hr Urine Collection: Process/Ship				х						х													
Pregnancy Form ³		×																					
Mini-Mental State Exam		x																					
PD Features		x																					
Diagnostic Features - PD																		x		x			
Primary Diagnosis																		х		х			
MDS-UPDRS Parts I-III		x		×	x	x	x	x	x	х	x	×	x	x				x		x			
MDS-UPDRS Part IV (as warranted)						±	±	±	±	±	±	±	±	±				x		x			
Modified Hoehn & Yahr		х		х			х			x				x				х		х			
Modified Schwab & England ADL and PDQ-39				×			×			x				×				x		x			
NeuroQOL		x																х					
Depression module of NeuroQOL				х			х			x				x									
MoCA (cogntion test)				x			х			x				x				×		х			
RBD Question	x			×			х			x				x				x		х			
Assess Need for Dopaminergic Therapy ⁴				х	x	x	x	x	×	x	х	×	x	x	х		x	x	x	х	x		
Concomitant Medication Log		×		×	×	×	х	×	×	x	х	×	×	x	×		x	×	×	х	x		
Adverse Event Log ⁵		×		×	×	x	х	×	x	x	х	×	x	x	×		x	x	×	х	x		
Randomization to Med Assign				×																			
Dose Management Log				×	×	×	х	×	×	x	х	×	×	x					×	х			
Study Drug Dispensing/Return Log				x	×	x	x	×	x	x	x	×	x	x						x			
PD-EQ				×																			
Blindedness Questionnaire						×								x					±	x			
Post Visit Telephone Call Regarding Eligibility and DAT Scan	×	×	×																				
Post Visit Telephone Call to Adjust Dose					×	×	×	×	×	x	×	×	×										
Conclusion of Study Participation																		x				x	

¹Optional (opt-in) study ²Safety lab samples sent to central laboratory

³For women of child-bearing potential; repeated at other times if clinically indicated

⁴Once need for dopamineraic therapy has been determined, no longer complete the form at future visits ⁵For subjects that discontinue study participant prior to Month 27, AEs active at the time the subject discontinues participation should be followed for 30 days post discontinuation or until resolved or stablized (whichever comes first) as long as the subject agrees to the follow-up.

⁶DAT scan may not be conducted until SC lab results are reviewed; and Baseline visit may not be conducted until SC lab results and DAT scan results are reviewed ⁷End of study DAT scan will only be conducted with subjects who have consented to the additional DAT scan. ± = Optional as specified in protocol

3. Statistical Design

3.1 Primary Outcome

Our choice of rate of change in MDS-UPDRS I-III total score as our primary efficacy measure is based on an interest in an outcome that can be evaluated within 2 years and an interest in a patient-reported outcome. Moreover, our preliminary data from the SURE-PD trial (NCT NCT00833690) showed dosage-dependent efficacy of serum urate elevation for 24-month change in UPDRS I-III total score. Anticipating that recruitment will require 18 months, evaluations of the primary outcome needs to be completed in 2 to 2.5 years in order to launch, implement, and publish results from the trial within a 5-year grant period.

Assessing change in MDS-UPDRS or other measures of motor symptoms among initially de novo PD patients becomes more complex as subjects begin initiating dopaminergic therapy, with roughly two-thirds expected to have initiated dopaminergic therapy by 2 years in the placebo group. We feel that assessing motor symptoms when not on dopaminergic therapy best reflects the efficacy of the intervention under study, whereas evaluation in the OFF condition after dopaminergic therapy has already been initiated is burdensome to subjects and unreliable due to incomplete and variable wash-out. Evaluating motor symptoms in the ON condition is prone to bias due to adjustment of dopaminergic therapy to achieve a pre-targeted level of symptoms. We propose instead to analyze MDS-UPDRS measurements made prior to initiating dopaminergic therapy, considering use of such treatments a censoring event that precludes observation of future untreated MDS-UPDRS scores. While delaying progression over only 2 years provides less benefit to patients than we would ultimately wish to offer, we feel that a demonstration of delay over 2 years in the absence of symptomatic effects is an achievable result, one that could provide evidence of disease modification early in the clinical course, and may motivate a longterm trial focused on functional and quality of life endpoints.

3.2 Efficacy Outcomes

Additional efficacy outcomes will include time to disability warranting dopaminergic therapy, the prescribed levodopa equivalent dosage (LEDD), motor function as measured by MDS-UPDRS part III, ambulation subset, and patient-reported sections (IB and II), striatal DAT binding by DaTscanTM, cognition as measured by MoCA, mood as measured by Neuro-QOL Depression, quality of life as measured by PDQ-39, and functional disability as measured by modified Schwab and England. Measures of parkinsonian symptoms assessed by the MDS-UPDRS will be analyzed in two ways: (a) excluding assessments completed after initiation of dopaminergic medication, and (b) adjusting for time-dependent LEDD.

3.3 Safety Outcomes

Safety of oral inosine titrated to achieve trough serum urate in the range 7.1 to 8.0 mg/dL will be evaluated by comparing active vs. placebo treatment groups with respect to overall adverse event (AE) and serious adverse event (SAE) rate, time to first SAE, and proportions of subjects experiencing (a) each type of AE, classified by Medical Dictionary for Regulatory Activities (MedDRA) preferred term and system organ class, (b) clinically-significant abnormal labs, and (c) clinically significant abnormal vital signs, including orthostatic hypotension defined as positional dizziness or other clinical symptoms of orthostatic hypotension or a drop in systolic

and diastolic blood pressures of 20 mm Hg and 10 mg Hg or more, respectively, when moving from a supine to a standing position.

3.4 Tolerability

Tolerance of treatment by an individual participant will be defined as remaining on-study and on his/her assigned treatment without one or more AE-associated dosage reductions lasting more than 4 weeks cumulative. Tolerability of oral inosine titrated to achieve trough serum urate in the range 7.1 to 8.0 mg/dL will be defined as the proportion of all participants in the active arm who are tolerant of the treatment at 12 weeks (short-term), 12 months (medium-term), and 24 months (long-term). Oral inosine titrated to achieve trough serum urate in the range 7.1 to 8.0 mg/dL will be declared tolerable for a given duration of treatment if the proportion who are tolerant is significantly greater than 50%.

3.5 Symptomatic Effects

Symptomatic effects will be estimated by changes in motor symptoms (a) during the first 3 months of wash-in at the start of period 1, and (b) during the 3-month wash-out during period 2 or at the end of study drug exposure, if earlier.

3.6 Two-period Evaluations

Analysis of the persistence of benefit after the 3-month wash-out of period 2 among subjects randomized to active treatment during period 1 permits an evaluation of disease-modifying effect of serum urate elevation. Not all measures are amenable to two-period evaluation because of the censoring effect of initiation of dopaminergic therapy. In particular, with only one-third of subjects expected to have not initiated dopaminergic therapy at the end of period 1, few data on uncensored MDS-UPDRS trajectories during wash-out will be available and subjects contributing those data are a non-random subset of slow progressors. For LEDD-adjusted analysis of MDS-UPDRS and other measures that are equally evaluable at the end of both periods, a three-part test of significantly slower worsening during period 1, non-inferior rates of worsening during period 2, and a significant net benefit at the end of period 2 would provide evidence of disease modification if all three evaluations were favorable.

3.7 Effect Size for Primary Outcome

[figure not shown]
The effect size for determining power is based on estimates of the minimum clinically important difference (MCID) for changes in MDS-UPDRS I-III total scores and on the previously observed association between baseline serum urate levels and the rate of change in UPDRS I-III total scores in the DATATOP, PRECEPT, and SURE-PD trials.

Hauser et al.¹ report that placebo-treated subjects who reported being minimally worse over 26 weeks on a global impression of change assessment experienced an average increase in UPDRS I-III total scores of 4.9 units. Given our expectation that elevated serum urate will delay progression, not improve symptoms, a MCID related to minimal worsening among placebo subjects seems most appropriate in this context. Based on estimates by Goetz and colleagues²⁻⁵ for PD patients with mild symptoms (Hoehn and Yahr stage I/II), MDS-UPDRS I-III total scores are roughly 30% larger than UPDRS I-III total scores (2.5x for 16 questions in Part 1, 1.1x for 52 questions in Part II, and 1.2x for 108 questions in Part III, yielding a weighted conversion of 1.29x), implying a MCID of 6.3 MDS-UPDRS I-III total score units.

We expect to enroll subjects with mean baseline serum urate of approximately 4.5 mg/dL based on data from SURE-PD and then raise levels in the active arm 3 mg/dL on average at trough sampling. A 3 mg/dL difference in baseline serum urate predicted 8.1 and 2.1 unit per year differences in UPDRS I-III total score slopes in the DATATOP⁶ and PRECEPT⁷ trials. In the SURE-PD trial⁸, subjects randomized to moderate serum urate elevation (7 to 8 mg/dL at random sampling) progressed 1.1 unit / year slower than placebo arm subjects with wide confidence bounds (95% CI 4.8 units / year slower to 2.8 units / year faster). Note that this estimate from SURE-PD (see protocol Fig. 7D) is conservative relative to an alternative model for the effect of serum urate elevation (see protocol Fig. 7C). A random-effects meta-analysis of results from the three studies yields a weighted estimate of 4.5 units slower progression in UPDRS I-III total score over 2 years among patients with higher serum urate levels.

We propose that 6.3 units over two years or a difference in slopes of 3.15 units per year is a reasonable minimum clinically important difference (MCID) in MDS-UPDRS I-III total scores, equal to a MCID of 4.9 units on the scale of UPDRS I-III total scores. This would correspond to a reduction of 20% of the expected placebo rate based on a random effects meta-analysis (Fig. 1 [from protocol Fig. 13]) of the mean rates of decline in UPDRS I-III total scores among de novo PD patients with baseline serum urate levels below 5.9 mg/dL in the DATATOP^{9,10}, PRECEPT¹¹, and SURE-PD⁸ cohorts. Changes in UPDRS I-III total scores were analyzed using random-slope mixed models censoring follow-up when dopaminergic therapy was initiated. The weighted mean estimate was 0.98 points / month or 23.5 points over 2 years with substantial heterogeneity in the estimate among studies (see Fig. 1).

3.8 Sample Size

urate. Early, largely untreated PD subjects with a serum urate of <5.9 mg/dL at baseline from DATATOP (n=155; double-placebo only), PRECEPT (n=446) and SURE-PD (n=25; placebo only) were followed for up to two years. The overall UPDRS rate was obtained by weighting each estimate by the inverse of its standard error.

Power for the primary outcome of rate of change in MDS-UPDRS I-III total score is based on a random slopes model with shared baseline. The model will include fixed effects of time, treatment x time, sex, sex x time, an indicator of baseline MAO-B inhibitor use, and baseline MAO-B inhibitor use x time and random site- and subject-specific intercepts and slopes, each with unstructured covariance. MDS-UPDRS assessments completed after a subject has initiated dopaminergic therapy will be censored.

Based on applying the same primary analysis model to data from SURE-PD, the following variance components were estimated for UPDRS I-III total scores: site-level variance (intercept = 9.75, slope = 0.0123 / month, covariance = -0.346), subject-level variance (intercept = 77.4, slope = 0.230 / month, covariance =2.87), and residual variance = 13.9. We assume that 70% of subjects will initiate dopaminergic therapy based on experience in SURE-PD plus up to 8% additional lost to follow-up prior to initiating dopaminergic therapy. With the planned schedule for MDS-UPDRS assessments (screening, baseline, 3 weeks, 6 weeks, 12 weeks, and then

quarterly through 24 months), the variance and censoring estimates above imply an effective standard deviation for UPDRS I-III total score slopes of 0.587 units / month or 0.758 units / month on the scale of MDS-UPDRS I-III total scores.¹²

Given a standard deviation of 0.76 units / month, a final two-sided test at alpha = 0.046 allowing conservatively for two interim analyses at alpha = 0.001 each, the study would have 80% power with n = 270 subjects randomized 1:1 to placebo or urate elevation if the true effect of treatment were to reduce the rate of increase in MDS-UPDRS I-III total score by 6.3 points over 2 years.

This estimate of power is robust to variable sex-specific enrollment rates and treatment efficacy as long as the average effect of treatment across sexes in the ratio enrolled is 6.3 points over 2 years (Fig. 2A). If urate elevation reduces the average rate of progression by 6.3 points over 2 years only among male or female participants and the other sex experiences less benefit, power would be lower (Fig. 2B). This is unavoidable if a large proportion of the enrolled population accrues less benefit from the intervention. Conversely, power would be greater than 80% if one sex experiences a benefit greater than 6.3 points over 2 years and the other sex experiences at least that large a benefit.

[figure not shown]

Figure 2. (A) Power for the primary aim across a range of sex-specific treatment responses, all cases with the average treatment response across sexes equal to the MCID of 6.3 points over 2 years. Note that equal prevalence of male (M) and female (F) participants is plotted, but the power curve for other prevalence ratios are so similar as to be indistinguishable at this scale. (B) Power for the primary aim when the effect of treatment on one sex is equal to the MCID and the effect on the alternate sex varies from 50% to 150% of MCID for a range of different prevalence ratios.

3.9 Power for Secondary Outcomes

The trial will have an 80% probability of observing at least one instance of any class of adverse event expected to occur in at least 1.2% of individuals receiving inosine. The trial will have 80% power to detect increased risk of any class of adverse event among subjects receiving inosine if the true risk is two-fold higher and the expected proportion among placebo subjects is at least 14% or if the true risk if four-fold higher and the expected proportion among placebo subjects is at least 3.4%. The trial has 80% probability of declaring serum urate elevation tolerable if the true proportion tolerant under the definition given in Sec. 3.4 at 12 weeks, 12 months, and 24 months is at least 62%.

The estimated SE for symptomatic effects on UPDRS I-III total scores during wash-in between the moderate elevation and placebo arms in the SURE-PD trial was 0.53 units / month. With n = 25 subjects per treatment group in SURE-PD, the expected SE for estimating symptomatic effects in this trial will be roughly sqrt (25/135) * 0.53 = 0.23 units / month. With that SE, the trial would have 80% power to detect symptomatic effects on the order of a difference in slopes during wash-in or wash-out of 0.65 units/month.

The Kaplan-Meier product-limit estimate from the SURE-PD trial of the proportion of placebo subjects requiring dopaminergic therapy by 24 months was 62%. Assuming constant hazard at the same rate among placebo subjects in this trial during period 1 (0 to 24 months) and 8% loss to follow-up prior to determining need for dopaminergic therapy, the trial will have 80% power to detect a hazard ratio of 0.62. Extrapolating to 27 months, we expect a total of 67% of placebo arm subjects to have disability warranting dopaminergic therapy at the end of period 2 (24 to 27 months). The study would have 80% power to detect a difference in the proportion of subjects with disability warranting dopaminergic therapy if 50% or fewer of active arm subjects have progressed by the end of the trial.

Given preliminary data from SURE-PD on the variance components from random-slope models for MoCA after Rasch score conversion, GDS-15, and S&E ADL, the effective standard deviations (in points per month) for these measures given our planned follow-up schedule are 0.038, 0.097, and 0.31, respectively. Weaver et al.¹³ report an among-person standard deviation for PDQ-39 at 24 months after deep brain stimulation of 14.2 to 15.3. Assuming conservatively no within-person covariance, that would imply a standard deviation for 24-month change of approximately 30. Given these estimates, the trial will have 80% power to detect 2-year treatment differences on these outcomes as small as 0.31, 0.80, 2.5, and 10.3, respectively.

4. Baseline Characteristics, Study Endpoints, and Final Disposition

4.1 **Baseline Characteristics**

Each analysis sample will be summarized overall and by treatment group for the following characteristics: randomization site; age, sex, race, ethnicity, time since symptom onset, time since PD diagnosis, modified Hoehn and Yahr score, resting tremor, use of an MAO-B inhibitor, serum urate, MDS-UPDRS scores, NeuroQoL module scores, years of education, MMSE, MOCA score, PDQ-39 score, modified Schwab and England ADL score, smoking history, caffeine consumption, sense of smell, RBD history, vigorous physical activity, serum urate, DAT ligand uptake, BMI, supine systolic and diastolic blood pressure, and orthostatic hypotension.

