## 10.3.3 Secondary Outcomes

The trial will have an 80% probability of observing at least one instance of any class of adverse event expected to occur in at least 1.2% of individuals receiving inosine. The trial will have 80% power to detect increased risk of any class of adverse event among subjects receiving inosine if the true risk is two-fold higher and the expected proportion among placebo subjects is at least 14% or if the true risk if four-fold higher and the expected proportion among placebo subjects is at least 3.4%. The trial has 80% probability of declaring serum urate elevation tolerable if the true proportion tolerant under the definition given in Sec. 10.2.2.2 at 12 weeks and 24 months is at least 62%.

The estimated SE for symptomatic effects on UPDRS I-III total scores during wash-in between the moderate elevation and placebo arms in the SURE-PD trial was 0.53 units / month. With n=25 subjects per treatment group in SURE-PD, the expected SE for estimating symptomatic effects in this trial will be roughly sqrt (25/135) \* 0.53 = 0.23 units / month. With that SE, the trial would have 80% power to detect symptomatic effects on the order of a difference in slopes during wash-in or wash-out of 0.65 units/month.

The Kaplan-Meier product-limit estimate from the SURE-PD trial of the proportion of placebo subjects requiring dopaminergic therapy by 24 months was 62%. Assuming constant hazard at the same rate among placebo subjects in this trial during period 1 (0 to 24 months) and 8% loss to follow-up prior to determining need for dopaminergic therapy, the trial will have 80% power to detect a hazard ratio of 0.62. Extrapolating to 27 months, we expect a total of 67% of placebo arm subjects to have disability warranting dopaminergic therapy at the end of period 2 (24 to 27 months). The study would have 80% power to detect a difference in the proportion of subjects with disability warranting dopaminergic therapy if 50% or fewer of active arm subjects have progressed by the end of the trial.

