## 10.5.7 Safety and Tolerability Outcomes

Overall AE and SAE rates will be compared between treatment groups by negative binomial regression. Time to first SAE will be compared between treatment groups by Kaplan-Meier logrank test. The proportion of subjects experiencing (a) each type of AE, classified by MedDRA preferred term and system organ class, (b) clinically-significant abnormal labs, and (c) clinically significant abnormal vital signs, including orthostatic hypotension defined as positional dizziness or other clinical symptoms of orthostatic hypotension or a drop in systolic and diastolic blood pressures of 20 mm Hg and 10 mg Hg or more, respectively, when moving from a supine to a standing position will be compared between treatment groups by Fisher's exact test.

Assuming no administrative censoring, all subjects will be classifiable as tolerant or intolerant, with subjects lost to follow-up or withdrawing consent classified as intolerant. Tolerability will then be estimated by simple proportions tolerant at 12 weeks and 24 months. Serum urate elevation will be declared tolerable at each time point if its exact one-sided lower 95% confidence bound is greater than 50%. If evaluation of tolerance is censored, then Kaplan-Meier product-limit estimates and their complementary log-log confidence bounds will be used. We will explore the relationship between tolerance and use of dopaminergic therapy using Cox regression with use of dopaminergic therapy as a time-dependent covariate.

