4.6 Tolerability Endpoint

Tolerance of treatment by an individual participant will be defined as remaining on-study and on his/her assigned treatment without one or more AE-associated dosage reductions lasting more than 4 weeks cumulative. Tolerance will only be assessed through 24 Oct 2018, the day before clinical sites were notified of early study closeout, as discontinuation of study drug after that date may reflect a change in participants' or investigators' equipoise. Tolerability of oral inosine titrated to achieve trough serum urate in the range 7.1 to 8.0 mg/dL will be defined as the proportion of all participants in the active arm who are tolerant of the treatment at 12 weeks (short-term), 12 months (medium-term), and 24 months (long-term). Oral inosine titrated to achieve trough serum urate in the range 7.1 to 8.0 mg/dL will be declared tolerable for a given duration of treatment if the proportion who are tolerant is significantly greater than 50%.

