6.7.5 Tolerability

Participants will be classified as tolerant, intolerant, or censored with subjects lost to follow-up or withdrawing consent prior to administrative termination classified as intolerant. Tolerability will then be estimated from Kaplan-Meier product-limit methods with complementary log-log confidence bounds at 12 weeks, 12 months, and 24 months. Serum urate elevation will be declared tolerable at each time point if its one-sided lower 95% confidence bound is greater than 50%. We will explore the relationship between tolerance and use of dopaminergic therapy using Cox regression with use of dopaminergic therapy as a time-dependent covariate.

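### The stated 80% chance of declaring inosine tolerable at a true 62% does not belong to the written one-sided 95% rule, which gives 86% with complete follow-up, and no separate 24-month figure allows for the October 2018 cut-off

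*SAP*

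**What the plan says.** The power statement in SAP 3.9 begins "The trial has 80% probability of declaring serum urate elevation tolerable if the true proportion tolerant under the definition given in Sec. 3.4". It then names three time points (12 weeks, 12 months and 24 months) and puts the threshold for the true proportion at 62%. Protocol 10.3.3 opens the same way, "The trial has 80% probability of declaring serum urate elevation tolerable if the true proportion tolerant", with the same 62%, for 12 weeks and 24 months.

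The definition it refers to, SAP 3.4, requires the tolerant proportion to be significantly above 50%. It gives no significance level and does not say whether the test is one- or two-sided. Protocol 10.2.2.2 is equally silent.

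The level appears only in the analysis sections. SAP 6.7.5 uses Kaplan-Meier estimates with complementary log-log bounds and declares treatment "tolerable at each time point if its one-sided lower 95% confidence bound is greater than 50" per cent. Protocol 10.5.7 sets the same level with an exact bound: "Serum urate elevation will be declared tolerable at each time point if its exact one-sided lower 95% confidence bound is greater than 50" per cent.

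SAP 4.6 adds that "Tolerance will only be assessed through 24 Oct 2018", the day before sites were told of early closeout. SAP 6.7.5 accordingly allows participants to be classed as censored.

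**The concern.** This sentence is the only operating characteristic given for a formal pass-or-fail declaration at each time point. If it was computed at a different level from the one written, the reader cannot tell whether a 95% or a 97.5% one-sided bound was meant. With 135 participants the two rules differ by two tolerant participants at the decision point (78 against 80).

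The single figure also covers nearly complete 12-week data and truncated 24-month data. SAP 5.15 provides for a visit standing in for month 24 because of early closure, so the SAP itself expects some participants not to reach month 24. The power sentence was not revised for that.

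**Working it through.** **Inputs.**
- Arm size 135: SAP 3.8 plans the trial "with n = 270 subjects randomized 1:1 to placebo or urate elevation", and SAP 3.9 uses 135 per arm in "the expected SE for estimating symptomatic effects in this trial will be roughly sqrt (25/135) * 0.53 = 0.23 units / month".
- Null proportion 0.50; true proportion 0.62.
- Loss to follow-up before administrative termination counts as intolerant (SAP 6.7.5), so it does not reduce the denominator.

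**1. Reproducing the printed 80%.** For a one-sample test with null variance under the null, power = Φ{[0.12 − z·√(0.25/135)] / √(0.62·0.38/135)}, with √(0.25/135) = 0.0430 and √(0.2356/135) = 0.0418.
- One-sided 2.5% (z = 1.960): (0.12 − 0.0843)/0.0418 = 0.85, so power is 0.803. This matches the plan. The exact binomial at this level needs 80 tolerant and gives 0.773.
- One-sided 5% (z = 1.645): (0.12 − 0.0708)/0.0418 = 1.18, so power is 0.881. This does not match.

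Other approximations at one-sided 5% also miss 80%: 0.862 with continuity correction, 0.879 by arcsine and 0.890 by Wald.

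**2. The written rule with complete follow-up.**
- Exact bound (protocol 10.5.7): the smallest count whose one-sided lower 95% bound exceeds 0.50 is 78. P(X ≥ 78 | 0.50) = 0.042 and P(X ≥ 78 | 0.62) = 0.864.
- Complementary log-log bound (SAP 6.7.5), without censoring: the lower bound is p^exp(1.645·s), where s = √[(1−p)/(np)] / |ln p|. At 78/135, p = 0.5778, s = 0.134 and the bound is 0.505. At 77/135 it is 0.497. The critical count is again 78, so power is again 0.864.
- Setting P(X ≥ 78 | p) = 0.80 gives p = 0.609.

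**3. The cut-off.** Neither document gives enrolment dates or the follow-up distribution at 24 October 2018, so everything here rests on assumptions. Accrual is taken as uniform over the 18 months planned in SAP 3.1, with a true 62% tolerant at 24 months. The SAP's Kaplan-Meier rule was simulated 10,000 times per cell. The earliest start shown is the date of protocol version 2.0 (1 December 2015, 34.8 months before the cut-off), which is not an enrolment date.

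| Accrual starts (months before cut-off) | Follow-up range (months) | Share able to reach month 24 | Power, constant hazard | Power, intolerance earlier | Power, intolerance later |
|---|---|---|---|---|---|
| 34.8 | 16.8–34.8 | 60% | 0.835 | 0.850 | 0.805 |
| 30 | 12–30 | 33% | 0.752 | 0.800 | 0.676 |
| 27 | 9–27 | 17% | 0.638 | 0.722 | 0.537 |
| 26 | 8–26 | 11% | 0.600 | 0.689 | 0.492 |
| 24.7 | 6.7–24.7 | 4% | 0.558 | 0.649 | 0.453 |

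With accrual starting 28 or 30 months before the cut-off, power at a true 62% stays at about 0.85 to 0.87 for both 12 weeks and 12 months.

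**The case against.** The strongest reply is that 80% is not a miscalculation. It is the ordinary two-sided 5% answer, SAP 3.4 leaves the level open, and with complete follow-up it understates power. All of that stands: the defect is a mismatch of level between sections, not faulty arithmetic.

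The analysis also handles truncation properly. Censoring with Kaplan-Meier bounds widens the interval where information is lost, and the power figure changes no estimate or decision. That stands too, although the SAP still prints the figure as a property of its 24-month declaration.

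The practical effect is modest. Under the constant-hazard model, with accrual starting 27 to 34.8 months before the cut-off, 24-month power at a true 70% is between 95% and 99.9%. The loss matters mainly when the true proportion is near 62%.

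A reader might infer two stronger points, and the documents support neither. One is that the 80% is wrong in both directions, too low early and too high at 24 months. The 24-month scenarios straddle 80%: the earliest accrual considered gives about 84% under a constant hazard. The other is that missing the 24-month bound would be reported as intolerance. The rule only permits a declaration of tolerability, and no section equates a missed bound with its opposite.

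**Conclusion.** The power statement does not belong to the plan's own rule. With 135 inosine participants and complete follow-up, the rule gives 86.4% at a true 62%, about 6 points above the printed 80%, and reaches 80% at about 61%. This rests only on the arm size and the written bound, and it holds closely at 12 weeks and 12 months in the accrual scenarios run.

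At 24 months the cut-off reduces power, and SAP 3.9 makes no allowance for it. The size of the reduction cannot be read from the documents. The 0.64 to 0.84 obtained with accrual starting 27 to 34.8 months before the cut-off is an illustration that depends on assumed dates, uniform accrual and a constant hazard. Its lower end is not a bound: the scenarios with later accrual or later intolerance go down to 0.45.

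Tolerability is a secondary outcome and the primary analysis is untouched. This is a minor point.

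**What to change.** - In SAP 3.4 and 3.9, state the one-sided 5% level so that they agree with SAP 6.7.5.
- In SAP 3.9, restate the power as about 86% at a true 62% (80% at about 61%), assuming complete follow-up, and say that this applies closely to 12 weeks and 12 months.
- Give 24 months a separate figure, computed from the blinded distribution of follow-up at 24 October 2018 with the assumed timing of intolerance stated. That distribution replaces the accrual assumptions used above.

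The cost is SAP wording and one blinded calculation. The decision rule, estimator and data collection do not change, and no new rule for interpreting a missed bound is needed. SAP section 1 makes the SAP authoritative on data analysis, so correcting it there is enough.
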